3.0 Inclusion/Exclusion Criteria

Inclusion Criteria

Criteria for inclusion will be:

- Age of 18 years or older
- Hospital admission for hypervolemic decompensated heart failure complicated by loop diuretic resistance.
 - Hypervolemia will be diagnosed by the admitting provider as either (i) pulmonary artery catheterization with a pulmonary capillary wedge pressure greater than 19mmHg plus a systemic physical exam finding of hypervolemia (peripheral edema, ascites, or pulmonary edema on auscultation) or (ii) in the absence of pulmonary artery catheterization data 2 of the following signs or symptoms: peripheral edema ascites, jugular venous pressure > 10mmHg, or pulmonary edema on chest x-ray.
 - Loop diuretic resistance is defined as a provider decision to pursue combination diuretic therapy because of failure to reach provider defined adequate diuresis (can not exceed urine output of 2 L in past 12 hours) despite receipt of an intravenous loop diuretic dose of a furosemide equivalent of at least 240mg/day over at least the past 12 hours (40mg furosemide = 20mg torsemide = 1mg bumetanide).
- Standard-of-care monitoring, including 24 hour telemetry monitoring on an inpatient ward and a basic metabolic panel laboratory assessment twice daily during the study period.

Exclusion Criteria

Candidates will be excluded if they meet any of the following criteria at the time of enrollment:

- Decision to pursue hemodialysis by a nephrologist
- estimated glomerular filtration rate by the MDRD equation < 15ml/min/m²
- systolic blood pressure < 85mmHg
- pregnancy* or breastfeeding
- serum potassium < 3.0mEq/L
- serum sodium > 145mEq/L or < 130mEq/L
- severe malnutrition
- advanced liver disease
- inability to perform standing weights
- inability to collect and measure urine with either a foley catheter or urine collection containers
- concomitant therapy with strong CYP3A4 inhibitors/inducers (systemic ketoconazole, clarithromycin, itraconazole, telithromycin, saquinavir, nelfinavir, ritonavir, neofodone, rifampin, rifabutin, rifapentin, phenytoin, phenobarbital, carbamazepine, St. John's Wort), p-glycoprotein inhibitors (cyclosporine, erythromycin, tacrolimus, dronedarone, quinidine, or verapamil)
- non-study diuretics (spironolactone doses >75mg/day, eplerenone > 75mg/day, non-study thiazides or loop diuretics, or systemic acetazolamide, triamterene, or amiloride therapy)
- Thiazide medication administered in the previous 24 hours prior to randomization

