5.5 Study Definitions

- Urine output: Total urine volume (ml) from time of study enrollment to 48 hours
- Hypokalemia: Serum potassium value < 3.5mEq/L
- Severe Hypokalemia: Serum potassium value < 3.0mEq/L
- Hyponatremia: Serum sodium value < 135mEq/L

- Severe Hyponatremia: Serum sodium value < 130mEq/L and a decrease of 5mEq/L or more from enrollment serum sodium
- Overcorrection of serum sodium: increase in serum sodium from baseline by ≥ 12 mEq/L in 24 hours, increase in >8 mEq/L in 12 hours, or receipt of intravenous fluids because of symptoms of overcorrection of serum sodium regardless of the numerical rise
- Hypomagnesiemia: Serum magnesium value < 2mEq/L
- Diuretic efficiency = 24hr urine output/ 24hr Lasix equivalents in milligrams
- Weight: Standing weight on the same scale as used for baseline weight measurement
- New Atrial Arrhythmia: A “new” diagnosis of atrial arrhythmia (includes atrial fibrillation, atrial flutter, ectopic atrial tachycardia) lasting > 30 seconds OR any atrial arrhythmia which causes hemodynamic instability (MAP < 60 and requiring intervention)
- New Ventricular Arrhythmia: Ventricular tachycardia lasting longer than 30 seconds, or frequent non-sustained VT causing hemodynamic instability with MAP < 60 mmHg requiring intervention or > 1 intra-cardiac defibrillation or external cardiac defibrillation shock or ventricular fibrillation requiring defibrillation
- Hypotension: SBP < 85 for 2 repeated measurements within 30 minutes or lasting at least 30 minutes or symptomatic hypotension necessitating clinical intervention (defined as vasopressor support, intravenous fluid boluses, or initiation of inotropes)
- Treatment failure: Patients requiring additional non-study diuretic (spironolactone doses >75 mg/day, eplerenone > 75 mg/day, non-study thiazides (at a dose of metolazone 2.5mg or greater equivalence) or loop diuretics, or systemic acetazolamide (for diuretic indication), triamterene, or amiloride therapy) at any time during the 48-hour randomization period. These patients will be considered treatment failures for the purpose of analysis of the primary endpoint and all secondary endpoints.
- Patients whose cardiologist adds inotropic or vasodilator medications will not be considered treatment failures. Patients who require an increase in the loop diuretic regimen will also not be considered treatment failures.

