6.0 Risks

This study will evaluate the addition of an oral thiazide, intravenous thiazide, or tolvaptan to augment intravenous loop diuretic therapy in patients with hypervolemic decompensated heart failure and diuretic resistance to adequately dosed loop diuretic monotherapy. Augmentation of loop diuretic therapy with a second diuretic (commonly a thiazide) is considered the standard-of-care in diuretic resistance and is endorsed by the AHA/ACCF and HFSA guidelines.^{8,9}

Tolvaptan

Several large scale clinical trials have demonstrated the safety of tolvaptan in patients with hypervolemic decompensated heart failure, including in those without hyponatremia. The EVEREST study evaluated 4,133 patients with decompensated heart failure randomized to placebo or tolvaptan for 60 days. The in-hospital serious adverse event rate was similar between tolvaptan (6.5%) and placebo (5.5%). The most common adverse effects of tolvaptan in these trials have been thirst (16%), dry mouth (8.4%), and polyuria. Hypernatremia occurred in 1.7% of tolvaptan patients vs 0.5% of placebo patients. Acute kidney injury, hypotension, and potassium derangements are not associated with tolvaptan therapy. As our duration of study is only 48 hours, it is not anticipated that study participation will be associated with increased risks beyond standard diuresis augmentation with a thiazide.

Hypernatremia/Over-correction of Serum Sodium

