While hyponatremia is not the target population of this study, patients with a serum sodium range of 130-145mEq/L are eligible to participate. Relative to the thiazide arm, patients with hyponatremia randomized to tolvaptan are at the unique, albeit rare, risk of over-correction of serum sodium. Overcorrection of sodium is commonly defined as an increase in serum sodium by more than 12mEq/L in 24 hours. Overcorrection of serum sodium is most likely to occur when the serum sodium is < 125mEq/L at baseline, which is an exclusion criterion of our study. The SALT studies included patients with hyponatremia (serum sodium < 135mEq/L) from various disease states, including heart failure. Only 5 patients (2.2%) of patients experienced a rise if serum sodium > 12mEq/L during any 24 hour time period, on a dose of 15mg to 60mg a day of tolvaptan. No patients experiencing this rapid correction and no patients in EVEREST developed osmotic demyelination syndrome (ODS). The FDA package insert for tolvaptan records that cases of ODS have occurred in post-marketing surveillance. In our study, we will only randomize 20 patients to tolvaptan, calculating to 1-2 patients with hyponatremia being randomized to tolvaptan. The low rate of overcorrection in literature, small sample size, exclusion criteria (sodium < 130mEq/L, advanced liver disease, severe malnutrition), short duration of therapy in our trial, and twice daily serum sodium monitoring makes the risk of a patient experiencing overcorrection of serum sodium low in our study. All patients will be hospitalized for the duration of the study and will be monitored for neurologic symptoms.

To minimize this risk, patients who are at highest risk of ODS at enrollment (serum sodium < 130mEq/L) will receive a serum sodium assessment 12 hours after the first dose of study diuretic. If the serum sodium increases > 8mEq/L from baseline at 12 hours, they will receive protocolized management to prevent ODS.

- 1) Intravenous D5W at 3ml/kg/hr
- 2) Repeat serum sodium every 2 hours
- 3) Neurologic monitoring for symptoms such as speech disturbances, altered mental status, and seizure activity
- 4) D5W and every 2 hour serum sodium labs will be continued until the serum sodium is < 8mEq/L above baseline sodium

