7.2 Reporting of SAE

All serious adverse events occurring from randomization through the 30 day follow-up period will be collected. The Site Investigator is responsible for monitoring the safety of patients enrolled into the study. The following adverse events are anticipated, disease related-events in patients with decompensated heart failure however they should still be reported on the Serious Adverse Event form in the REDCAP Database (some may require reporting as study endpoints):

- New Atrial Arrhythmia: A “new” diagnosis of atrial arrhythmia (includes atrial fibrillation, atrial flutter, ectopic atrial tachycardia) lasting > 30 seconds OR any atrial arrhythmia which causes hemodynamic instability (MAP < 60 and requiring intervention)
- New Ventricular Arrhythmia: Ventricular tachycardia lasting longer than 30 seconds, or frequent non-sustained VT causing hemodynamic instability with MAP < 60 mmHg requiring intervention or > 1 intra-cardiac defibrillation or external cardiac defibrillation shock or ventricular fibrillation requiring defibrillation
- Hypotension: SBP < 85 for 2 repeated measurements within 30 minutes or lasting at least 30 minutes or symptomatic hypotension necessitating clinical intervention (defined as vasopressor support, intravenous fluid boluses, or initiation of inotropes)
- Myocardial infarction: a cardiac event including an elevation in troponin above baseline with or without ECG changes that is judged to be a myocardial infarction by the treating attending cardiologist
- Cardiac arrest: any ventricular arrhythmic or pulseless electrical event that requires immediate life-sustaining medical therapies
- Acute renal failure: A rise in serum creatinine of 1 mg/dl or more from the baseline serum creatinine in the 48 hour treatment period
- Acute renal failure requiring dialysis: an acute renal failure event that began during the 48 hour study period and necessitates new hemodialysis during the hospitalization

- Worsening heart failure: the need for rescue therapy (additional open label loop diuretic, spironolactone doses >75mg/day, eplerenone > 75mg/day, non-study thiazides (at a dose of metolazone 2.5mg or greater equivalence), systemic acetazolamide (for diuretic indication), triamterene, amiloride, ultrafiltration, hemodialysis, or mechanical circulatory or respiratory support) in the 48 hour treatment period
- Death
- Metabolic SAE (during 48 hour treatment period):
 - Severe Hypokalemia: Serum potassium value < 3.0mEq/L

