 - Severe Hyponatremia: Serum sodium value < 130mEq/L and a decrease of 5mEq/L or more from enrollment serum sodium
 - Overcorrection of serum sodium: increase in serum sodium from baseline by ≥ 12 mEq/L in 24 hours, increase in >8mEq/L in 12 hours, or receipt of intravenous fluids because of symptoms of overcorrection of serum sodium regardless of the numerical rise
 - Hyperkalemia: serum potassium value > 5.5mEq/L
 - Gout: acute gout attack requiring treatment with an anti-inflammatory agent

All serious adverse events must be recorded in the Serious Adverse Event Record of the patient's REDCAP database. All serious adverse events should be monitored until stabilization or resolution.

Reporting to Local IRB. Investigators are also responsible for promptly reporting unexpected adverse events (serious and non serious) to their reviewing IRB in accordance with local requirements. The Vanderbilt investigational site will report DSM reports to the Vanderbilt IRB annually at the time of continuing review at a minimum. If 5 unexpected SAEs occur, the trial will be temporarily halted and the Vanderbilt IRB will be informed. After review, the study will resume if the IRB approves continuation with or without alterations in the study protocol.

Reporting to the Industry Sponsor

The investigator will notify the Sponsor within 24 hours of being notified of any SAE. The investigator will also notify the Sponsor of any pregnancy during the study period within 3 days of being notified. For all non-serious adverse events, the investigator will notify the Sponsor of all events as a line item list at the end of the study.

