9.0 Statistical Considerations

9.1 Sample Size

The study will have a sample size of 60 patients, equally allocated to the three study treatment groups.

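### Hypernatremia, which the protocol cites as more frequent with tolvaptan, has no definition, no automatic SAE level and no incidence by arm

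*Combined protocol and SAP*

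**What the plan says.** **Risk.** Section 6.0 states: "Hypernatremia occurred in 1.7% of tolvaptan patients vs 0.5% of placebo patients". The source is described there as follows: "The EVEREST study evaluated 4,133 patients with decompensated heart failure randomized to placebo or tolvaptan for 60 days". The next risk subsection names hypernatremia and overcorrection together in its heading, but its text deals only with overcorrection.

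**Eligibility.** Section 3.0 excludes "serum sodium > 145mEq/L or < 130mEq/L", so entry sodium may lie anywhere from 130 to 145 mEq/L.

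**Definitions.** Section 5.5 defines hypokalemia, severe hypokalemia, hyponatremia, severe hyponatremia, hypomagnesemia and overcorrection of serum sodium. The numerical limbs of overcorrection are "increase in serum sodium from baseline by ≥ 12 mEq/L in 24 hours, increase in >8 mEq/L in 12 hours". A third limb is met when intravenous fluids are given for symptoms of overcorrection. Hypernatremia is not defined.

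**Metabolic SAEs.** The list in section 7.2 holds severe hypokalemia, severe hyponatremia, overcorrection, gout and "Hyperkalemia: serum potassium value > 5.5mEq/L". It has no high-sodium level.

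**Outcomes.** Section 5.4 lists the incidence of severe hypokalemia. Sodium appears only as mean change at 24 hours, 48 hours and discharge. Appendix A schedules a basic metabolic panel (BMP) at 12, 24, 36 and 48 hours.

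**The concern.** Potassium has an absolute SAE limit at each end. Sodium has an absolute limit at the low end only, and at the high end just a rate of rise. The missing limit is the one for a harm that the protocol's own figures show to be more frequent with tolvaptan.

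Overcorrection does not stand in for it. Section 6.0 presents overcorrection as a risk for patients who start with hyponatremia, and expects only 1 or 2 of the 20 tolvaptan patients to be in that group. For the other 18 or 19, the more relevant question is how high the sodium goes, and no criterion addresses that.

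A mean change cannot show how many patients crossed a high level. The mean-change outcome also leaves out the 12- and 36-hour values that are drawn anyway. Without a prespecified definition, any later count would rest on a cut-off chosen after the data were seen. At stake are the completeness of safety capture and the balance of the electrolyte reporting under Aim 2.

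**Working it through.** **The plan's own design figure.** The plan gives no expected number of hypernatremia cases. Its one design figure is 82.3% power for weight change. A two-sample t test with 20 per arm, a difference of 1.5 kg, an SD of 1.6 kg and two-sided alpha 0.05 gives 82.4%, so that figure reproduces. This point does not depend on it.

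**Can sodium become high without meeting a numerical limb?** I take hypernatremia as sodium above 145 mEq/L. That is an assumption, borrowed from the exclusion limit in section 3.0. In whole mEq/L, the limbs need a rise of at least 9 within 12 hours or at least 12 within 24 hours.

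| Entry sodium | Rise needed to reach 146 | Level that meets the 12-hour limb | Level that meets the 24-hour limb |
|---|---|---|---|
| 138 | 8 | 147 | 150 |
| 140 | 6 | 149 | 152 |
| 145 | 1 | 154 | 157 |

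- From any entry value of 138 to 145, passing 145 takes a rise of 8 down to 1. That is below both limbs even if it all happens within 12 hours.
- From 145, a path of 151 at 12 hours (+6) and 156 at 24 hours (+5 more) gives a 24-hour rise of 11. Neither limb is met. This path shows how far the rule reaches. The documents do not say how likely it is.

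**How many cases might be involved?** Inputs are 1.7% and 0.5% (section 6.0) and 20 per arm (section 9.1: "The study will have a sample size of 60 patients, equally allocated to the three study treatment groups"). The rates come from 60 days of exposure and this trial lasts 48 hours, so applying them here is an assumption.

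- Ratio of the cited rates: 1.7 / 0.5 = 3.4.
- Tolvaptan rate: 20 × 0.017 = 0.34 expected cases; chance of at least one = 1 − 0.983^20 = 29%.
- Placebo rate: 20 × 0.005 = 0.10 expected cases; chance of at least one = 1 − 0.995^20 = 9.5%.
- Difference: 0.34 − 0.10 = 0.24 of a patient.

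**Could a test show a difference?** With 20 against 20, Fisher's exact test gives p = 0.106 for 4 against 0 and p = 0.047 for 5 against 0, so at least 5 against 0 is needed. Power at the cited rates is about 0.002%, and 80% power would need about 1,185 per arm. The documents give no 48-hour rate, so I show a range of assumed tolvaptan rates against 0.5%:

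| Assumed tolvaptan rate | Expected cases in 20 | Chance of at least one | Fisher power |
|---|---|---|---|
| 5% | 1 | 64% | 0.2% |
| 10% | 2 | 88% | 3.9% |
| 20% | 4 | 99% | 34% |

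**The case against.** A reader might infer that the SAE list counts thiazide harms and spares tolvaptan, so that the safety tally is tilted or a planned comparison is biased. The documents do not support that, for four reasons.

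- Overcorrection, which section 6.0 calls a risk unique to tolvaptan relative to the thiazides, is both defined and a metabolic SAE. Hyperkalemia is also listed and is not among the thiazide risks named in section 6.0.
- Neither section 5.4 nor section 9.3 plans a between-arm comparison of metabolic SAEs. The list is a reporting rule. Among outcomes, low and high sodium are treated alike: neither has an incidence.
- The advantage that Aim 2 expects for tolvaptan is less potassium repletion, which the classification of high sodium cannot affect.
- A high sodium is not barred from SAE reporting. The general criteria in section 7.0 cover events needing intervention to prevent permanent impairment, and important medical events by judgment. Any SAE goes to the sponsor within 24 hours, and non-serious events go on a line listing at study end.

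It is also fair to say that the cited rates come from a much longer exposure, that the expected counts are small, and that sodium values collected in every arm would allow a count later.

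All of this stands and limits the claim. It does not supply the missing piece. The general criteria depend on judgment, and an asymptomatic high sodium need not meet them. A count made later would lack a prespecified level.

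**Conclusion.** The plan has an asymmetric gap for absolute hypernatremia. It names the harm and cites a higher rate with tolvaptan, but provides no definition, no automatic SAE trigger and no incidence by arm. The overcorrection criterion leaves the gap open for patients entering at normal or high-normal sodium, up to a constructed case of 156 mEq/L at 24 hours.

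The absence of a high-sodium limit rests on the text alone. The size rests on two assumptions: 145 mEq/L as the reporting level, and 60-day rates carried over to 48 hours. On those, about 0.34 cases would be expected among 20 tolvaptan patients, against 0.10 per 20 at the placebo rate. That is too few for inference, although a single uncounted case is 1/20 = 5% of an arm. The correction is worth making because it is cheap and concerns a risk the protocol itself raises. The finding is about safety capture and balanced reporting. It is not evidence of bias in a planned analysis.

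**What to change.** 1. In section 5.5, define hypernatremia for reporting as serum sodium above the plan's own entry ceiling of 145 mEq/L.
2. In section 5.4, add the incidence of hypernatremia by arm beside that of severe hypokalemia. Count patients with any such value on the scheduled 12-, 24-, 36- and 48-hour BMPs, and present the counts descriptively.
3. In section 7.2, add a high-sodium entry to the metabolic SAE list at a level the sponsor sets. If the sponsor considers overcorrection sufficient, the protocol should say why.

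The cost is wording and a few more SAE forms. No further blood draws are needed.

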Patients will continue the loop diuretic therapy during this protocol. If the patient does not develop symptoms of ODS and responds to intravenous D5W therapy by hour 18 (6 hours after first serum sodium), they will be eligible for the scheduled second study diuretic dose at 24 hours. Patients experiencing any neurologic symptoms or who do not respond to intravenous D5W

therapy by hour 18 (6 hours after first serum sodium) will not be eligible for repeat study medication administration. All patients will be followed per the study protocol through Day 30.

Hepatic toxicity

Hepatotoxicity occurred in 3 patients in the TEMPO study, which evaluated the effects of Tolvaptan 60-120mg daily in a polycystic kidney disease patient population. In all 3 patients, the hepatic toxicity occurred after 3 months of therapy and resolved with tolvaptan discontinuation. Our study protocol will exclude patients with advanced liver disease, consistent with the updated FDA package labeling recommendations, and will administer a lower dose for only 48 hours.

Thiazides (Metolazone or Chlorothiazide)

In accordance with previous trials evaluating combination thiazide and loop diuretics (DOSE, CARRESS-HF), the metabolic risks include gout, hypokalemia, and hyponatremia. The risks include: hyponatremia, hypokalemia, gout flare/attack, and cardiac arrhythmias. In the CARRESS-HF study, ultrafiltration was compared to a step-wise diuretic protocol in 188 patients with hypervolemic, decompensated heart failure and worsening renal function. Of the 94 patients in the diuretic arm, 46% of participants received metolazone therapy. Only 3 (3%) patients experienced an electrolyte disorder, which included hypokalemia, hyponatremia, and hyperuricemia. Arrhythmic events were not specifically reported. A retrospective comparison of intravenous and oral thiazide diuretics found the rate of hypokalemia, defined as a serum potassium < 4mEq/L, to be 71% in the oral thiazide group and 83% in the intravenous thiazide group.¹⁴ Given the small size of previous combination diuretic studies, incidence rates of gout attacks and cardiac arrhythmias have not been quantified and are not provided in package labeling.¹¹ Our study will minimize hypokalemia and hyponatremia by monitoring the serum potassium and sodium every 12 hours during the study period. Electrolyte replacement will be performed at the discretion of the attending cardiologist, in accordance with standard of care practice.

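### Section 6.0 gives its D5W instruction for a rapid sodium rise only to patients with enrolment sodium below 130 mEq/L, a group the protocol excludes

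*Combined protocol and SAP*

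**What the plan says.** **Who can be enrolled.** Section 3.0, judged at enrolment, excludes "serum sodium > 145mEq/L or < 130mEq/L". Section 6.0 repeats this in two ways. It says that "patients with a serum sodium range of 130-145mEq/L are eligible to participate", and among its reasons for calling the overcorrection risk low it lists "exclusion criteria (sodium < 130mEq/L, advanced liver disease, severe malnutrition".

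**Who gets the pathway.** The next paragraph of Section 6.0 states that "patients who are at highest risk of ODS at enrollment (serum sodium < 130mEq/L) will receive a serum sodium assessment 12 hours after" the first study dose. It continues: "If the serum sodium increases > 8mEq/L from baseline at 12 hours, they will receive protocolized management to prevent ODS". That management is D5W at 3 ml/kg/hr, sodium every 2 hours and neurologic checks. The stop rule is: "D5W and every 2 hour serum sodium labs will be continued until the serum sodium is < 8mEq/L above baseline sodium". A patient without neurologic symptoms who "responds to intravenous D5W therapy by hour 18 (6 hours after first serum sodium" may have the study dose that Section 6.0 places at 24 hours.

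**Who is expected to be at risk.** Section 6.0 locates the risk in hyponatremic patients given tolvaptan and puts their number at 20 tolvaptan patients, "calculating to 1-2 patients with hyponatremia being randomized to tolvaptan". Section 5.5 defines hyponatremia as sodium below 135 mEq/L.

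**What applies to everyone.**
- Sections 5.6 and 6.0 and Appendix A give sodium every 12 hours.
- Section 6.0 gives neurologic monitoring.
- Sections 5.5 and 7.2 count a rise above 8 mEq/L in 12 hours as overcorrection at any baseline. Section 7.2 makes it a reportable serious adverse event, followed until it stabilises or resolves.
- Section 8.0 withdraws patients treated for overcorrection who have neurologic symptoms or have not responded to D5W within 6 hours, with no baseline limit.

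**The concern.** The pathway is offered as the measure that minimises a risk the protocol calls unique to tolvaptan. Its entry condition is one that no correctly enrolled patient can meet. In the start sentence, the pronoun for those who receive D5W can only refer to the group below 130 mEq/L.

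The practical consequence is narrow. If an eligible patient's sodium has risen by more than 8 mEq/L at 12 hours, the rise will be measured and reported. But no sentence that applies to that patient says to start D5W with two-hourly sodium. Section 8.0 then acts on failure to respond to D5W, which presupposes that someone started it. The decision falls to individual judgement. The team is blinded to whether the patient received tolvaptan, and for this risk the protocol had chosen a written procedure.

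**Working it through.** The plan gives no figure to reproduce here, so the check compares two ranges.

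**Inputs**

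| Item | Value | Source |
|---|---|---|
| Eligible enrolment sodium | 130 to 145 mEq/L | 3.0; restated in 6.0 |
| Pathway population | below 130 mEq/L at enrolment | 6.0 |
| Hyponatremia | below 135 mEq/L | 5.5 |
| Start trigger | rise above 8 mEq/L at 12 hours | 6.0 |
| Patients | 60 in all, 20 on tolvaptan | 9.1, 6.0 |
| Hyponatremic on tolvaptan | 1-2 (no derivation given; taken as stated) | 6.0 |

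**Step 1: overlap.** The ranges 130 to 145 and below 130 have no value in common, so 0 of 60 correctly enrolled patients enter the pathway. Both conditions are judged at enrolment, so drift between screening and baseline does not reconcile them.

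**Step 2: who is missed.** A patient who is both hyponatremic and eligible has sodium of at least 130 and below 135, that is 130-134 in whole numbers. On the protocol's own estimate this is 1/20 = 5% to 2/20 = 10% of the tolvaptan arm.

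**Step 3: would the absolute value show the problem?** Trigger level = baseline + 8. Baseline 130 gives above 138; baseline 134 gives above 142. Either result can still lie inside the 130-145 range, so only the change from baseline identifies the patient.

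**Step 4: which instructions survive without the pathway?**

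| Instruction | Applies to an eligible patient? |
|---|---|
| Measure sodium at 12 hours | Yes: 5.6, 6.0, Appendix A |
| Watch for neurologic symptoms | Yes: 6.0 |
| Report the rise and follow to resolution | Yes: 7.2 |
| Withdraw if symptomatic or unresponsive to D5W | Yes: 8.0 |
| Start D5W with two-hourly sodium | No: only in the 6.0 pathway |

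**Step 5: volume if triggered.** Over the 6-hour response window (hour 12 to hour 18), 3 ml/kg/hr × 6 h = 18 ml/kg. At an assumed body weight of 60-100 kg this is 1.08-1.80 L. The infusion stops on response, so the volume could be smaller. For comparison, Section 5.1 restricts fluid to 2 L/day and Section 9.2 takes 1.5 kg as the meaningful difference in 48-hour weight change.

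**The case against.** **The event is very unlikely.** Section 6.0 cites 2.2% of patients with a rise above 12 mEq/L in 24 hours in studies of patients below 135 mEq/L. Applied to 1-2 patients, that is 0.022 × 1 = 0.022 to 0.022 × 2 = 0.044 expected events. The trigger here differs (above 8 mEq/L at 12 hours), so the figure is only indicative. The point stands and limits the importance of the finding. It does not make the rule usable.

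**The pathway may be leftover text.** Section 6.0 also calls sodium below 125 mEq/L an exclusion criterion. Such patients are excluded, but the limit in Section 3.0 is 130. One could guess that the limit was once 125 and that the pathway served patients at 125-129, in which case deletion would be legitimate. The documents do not settle this. Deletion would, however, leave the D5W response rule in Section 8.0 with no start instruction anywhere.

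**Stronger readings that the documents do not support.**
- A reader might infer that enrolled patients are unprotected. They are not: everything in Step 4 except the start instruction still applies.
- A reader might count the missing resume rule as a second gap. Outside the pathway nothing holds study drug for a sodium rise, and Section 8.0 does not withdraw an asymptomatic responder. The resume rule therefore mostly restates the default of continued dosing.
- A reader might count the 18-19 tolvaptan patients with baseline 135-145 mEq/L, or hyponatremic patients in the thiazide arms, as wrongly left out. Section 6.0 places the risk in hyponatremic tolvaptan patients, so these others are outside the group it sets out to protect.

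**Conclusion.** The inconsistency is real and is plain from the text. The only instruction to start D5W with two-hourly sodium applies to 0 of 60 correctly enrolled patients and misses the 1-2 of 20 tolvaptan patients, at baseline 130-134 mEq/L, for whom the section expresses concern. That count rests on the protocol's own estimate. The conclusion also assumes a literal reading and correct enrolment; clinicians might well apply the pathway anyway.

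The gap is one of treatment instruction, not of detection, reporting or withdrawal. No event rate is claimed beyond the indicative figure above. Sample size, power and alpha are unaffected. It is worth correcting because a stated safety measure has an impossible entry condition and the repair is small.

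**What to change.** In Section 6.0, change the bracketed enrolment limit that opens the pathway from below 130 mEq/L to 130-134 mEq/L. In the same edit:

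- Where the text gives below 125 mEq/L as the exclusion criterion, state the actual limit, below 130 mEq/L.
- Align the second-dose-at-24-hours wording with Section 5.2, where blinded study doses are given every 12 hours and only active tolvaptan is next due at 24 hours. Say what happens to the hour-12 dose in a triggered patient.
- Cross-refer Sections 6.0 and 8.0 so that start, stop, resume and withdrawal read as one rule.

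**Cost.** This is a wording amendment. The 12-hour metabolic panel is already scheduled for every patient, so the check needs no new test. The downside is that a triggered patient with baseline 130-134 mEq/L receives D5W despite hypervolemia and fluid restriction, which may affect that patient's 48-hour weight, the primary outcome.

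Removing the baseline limit altogether would match the any-baseline definition in Sections 5.5 and 7.2. It would also extend D5W to hypervolemic patients with normal sodium, where the infused volume could again affect 48-hour weight. That choice belongs to the sponsor's clinicians and is not needed to repair the inconsistency.
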